7.2 Setting

The study population is identified using the Total Population Registry in each of the Nordic countries, for information on birth year, migration status, and date of death in each of the respective countries. The registries have full coverage of the Swedish, Danish, and Norwegian populations.

Nested case-control study (primary objective)

The study population is female residents of Sweden, Denmark, and Norway (ages 15-29 years) between 2006 and the latest years of coverage, in primary analysis focusing on those eligible/had a chance to get vaccinated before age 17 years. A description of the ages, birth cohorts, and calendar years of coverage for the included participants is provided in Table 1 and Figure 1.

Ecological study (secondary objective)

The study population is children, women and men living in Sweden, Denmark, and Norway (0-29 years of age) between the following calendar years and birth cohorts (Table 1):

- Sweden: 2000 2021 (birth cohort, 1971 2021)
- Denmark: 1997 2022 (birth cohort, 1968 2022)

PRODUCT: V501/V503	PROTOCOL/AMENDMENT VERSION NO.: V503-088-01-v1
REVOPS ID NO: NIS009722	CORE DRC APPROVAL DATE: 18JUL2024
EPIDEMIOLOGY NO.(PE STUDIES ONLY): EP08039.017	

• Norway: 2008 - 2022 (birth cohort, 1979 - 2022)

7.3 Inclusion Criteria

- The study subject must be alive and reside in Sweden, Denmark, or Norway as defined through the Total Population Registry of the respective countries at some point during the time period specified. Subjects will be censored at date of emigration (where applicable), and upon date of death (where applicable).
- The study subject must be of the appropriate age range (15-29 years) for AoRRP (primary objective).
- Only females are eligible to be included for the primary objective (due to low coverage of Gardasil vaccination among males during study period), whereas both genders are eligible to be included for the secondary objectives.
- To be considered as a potential case of RRP (for either primary or secondary objective), a study subject must have at least one first diagnosis of RRP (as defined in Section 7.1) in the appropriate country-specific registry, during the specified time period of focus.

7.4 Exclusion Criteria

- Subjects who receive a first diagnosis of RRP before age 15 will be excluded for primary analysis, as this more likely reflects a maternally transmitted juvenile-onset case, rather than a sexually transmitted adult-onset case.
- Subjects who immigrated to Sweden or Denmark after 2006, or to Norway after 2008, and age 9 years will be excluded as vaccination exposure status is unknown, and follow-up in registries may be insufficient to determine if incident case is truly new onset (primary objective).
- Subjects who receive the bivalent vaccine Cervarix (recombinant HPV bivalent [types 16 and 18] vaccine, GlaxoSmithKline) will be excluded since it provides no protection against the causative HPV types (6 and 11) in RRP (primary objective).

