There will be no adjustment for multiple comparisons in this study. Analyses have been prespecified, discriminating between primary and sensitivity analyses, and all results will be reported.

Secondary Objective: Calculation of Epidemiological Measure(s) of Interest

Annual age-standardized incidence rates (ASIRs) of JoRRP and AoRRP will be calculated, stratified by age group, gender, and calendar period and the p-values from the test for calendar year trends for these rates will be estimated. New cases of JoRRP or AoRRP will be the numerator for the calculation of incidence rates. The denominator will be the accumulated person-time in each calendar year for which the data are analyzed. As this is a highly robust measure over time and the entire population is sampled, it may not be necessary to include confidence intervals; however, given the small number of cases per calendar year, confidence intervals will be calculated.

Overall incidence rates will be adjusted for age according to European Standard Population, because of the larger proportion of older age groups in Nordic countries compared to the World Standard Population.

Exploratory Objective: Calculation of Epidemiological Measure(s) of Interest (e.g., hazard ratios, incidence rates, test/retest reliability)

Risk factors for AoRRP will be explored in the VE analysis conditional logistic regression model to evaluate if they are independently statistically significantly associated with the outcome of RRP, with all other factors held constant. Specifically, vaccination exposure will be at the reference level, i.e., the analysis of risk factor status will effectively be restricted to non-vaccinated individuals.

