Given that the main cause of RRP globally is infection with HPV type 6 or 11, results are expected to be generalizable. With the proposed study population design, there is restriction in analytical format as having access to the full baseline cohort will yield many technical advantages. The risk for misclassification of exposure to vaccination is minimized through the substantial in-house knowledge of combination of vaccination registries. Nonetheless there is a small but existing risk of non-differential misclassification of outcome. Generalizability is maximized through the population-based sampling frame and allowing all eligible study participants alive and resident in Sweden, Denmark, and Norway at the appropriate time to enter. Also, in recent years, especially the post-vaccination introduction era, Sweden, Denmark, and Norway have experienced high immigration, which may further increase generalizability of study results. The magnitude of random error is minimized in the

PRODUCT: V501/V503	PROTOCOL/AMENDMENT VERSION NO.: V503-088-01-v1
REVOPS ID NO: NIS009722	CORE DRC APPROVAL DATE: 18JUL2024
EPIDEMIOLOGY NO.(PE STUDIES ONLY): EP08039.017	

ecological study through including a very large group of subjects. Yet, it is acknowledged that the rarity of the outcome may lead to some challenges in precision, despite the large baseline study sample size.

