7.14 Methods to Minimize Bias

A register-based proxy for definition of outcome (JoRRP and AoRRP) will be used, i.e., ICD-10 code D14.1, which in Sweden is used to register the disease category "benign tumor of the larynx". To increase specificity, the full set of D14.1 cases available will be augmented with appropriate topography/morphology or SNOMED/Norpat codes when available, complete, and recommended by experts. Additionally, in sensitivity analyses, diagnostic and treatment codes described above will be applied to also improve specificity. Given that granulomas of the larynx are largely occurring in middle-age, male smokers, it is suggested that benign tumors of the larynx, other than HPV-associated papilloma, in the specified age ranges (i.e., 0-29 years) and restricted to females, will be very rare. If a misclassification of outcome due to using D14.1 would sometimes occur, it will likely lead to bias towards the null, which means that if vaccine effectiveness against RRP is observed, the true effect is likely greater.

Given the rarity of RRP, and the strong registration of healthcare in the Nordic countries, it is believed that virtually all cases of RRP will be identified by the above algorithm. The risk that a control selected at random from the underlying population is a false negative, i.e., a missed case of RRP, should be negligible.

All immigrant females to Sweden, Denmark and Norway (after age 9) will be excluded to ensure there is no misclassification of exposure, which removes the risk that subjects who have received HPV vaccination outside of these countries are mis-classified as non-vaccinated and ensures a minimum of six years of individual follow-up in the registries prior to case eligibility (at age 15) for exclusion of prevalent RRP cases.

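### The incidence series lacks the safeguard against imported, already-diagnosed disease that Section 7.4 gives the primary analysis, which can bias the calendar-year trend, probably toward a smaller decline

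*Protocol*

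**What the plan says.** Section 7.4 of the protocol states the exclusion: "Subjects who immigrated to Sweden or Denmark after 2006, or to Norway after 2008, and age 9 years will be excluded". It gives two reasons. One is that vaccination status is unknown. The other is that "follow-up in registries may be insufficient to determine if incident case is truly new onset (primary objective", and the parenthesis limits the rule to the primary objective. Section 7.14 explains the purpose of the age-9 cut: it "ensures a minimum of six years of individual follow-up in the registries prior to case eligibility (at age 15) for exclusion of prevalent RRP cases".

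The secondary, ecological part is defined more broadly:

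- Population (Section 7.2): "The study population is children, women and men living in Sweden, Denmark, and Norway (0-29 years of age", over the country-specific calendar periods.
- Residence (Section 7.3): alive and resident "at some point during the time period specified", with censoring at emigration or death.
- Case (Section 7.3), for either objective: "a study subject must have at least one first diagnosis of RRP (as defined in Section 7.1) in the appropriate country-specific registry".
- Numerator (Section 7.11): "New cases of JoRRP or AoRRP will be the numerator for the calculation of incidence rates". The denominator is person-time per calendar year, and a calendar-year trend test is planned.
- Stratification (Section 7.5): calendar year, gender and age.

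Section 5 says that incidence before and after Gardasil introduction is meant to give an ecological view of vaccine impact. Section 7.13 notes that "especially the post-vaccination introduction era, Sweden, Denmark, and Norway have experienced high immigration", and treats this only as a possible gain in generalizability.

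**The concern.** The first reason for the exclusion, unknown vaccination status, has no bearing on a series without an exposure. The second reason has nothing to do with vaccination. It concerns whether a recorded case is new, and an incidence numerator depends on that just as much as a case-control set does.

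RRP recurs. Section 5 says that nearly 20% of patients have aggressive disease needing more than 40 lifetime procedures. A person who arrives with existing disease may well be seen locally, and that record is then the first diagnosis in the country's registry and counts as a new case. The onset group can also be wrong. Someone diagnosed abroad in childhood who arrives after age 15 meets the AoRRP definition in Section 7.6.2, although the two secondary objectives exist to separate the two conditions.

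If such cases are more frequent in the later years, the later rates are raised relative to the earlier ones. A real fall after vaccine introduction would then look smaller in the series that is meant to show it.

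**Working it through.** **Step 1. Is there a safeguard elsewhere?** Sections 7.1 to 7.6, 7.11 and 7.14 and the Annex 2 shells give the incidence series no minimum residence, look-back, migration stratum or migration sensitivity analysis. Section 7.14 repeats the exclusion for females and ties it to vaccine exposure and to case eligibility at 15. Country of birth appears in Table 4 and in the adjustment list under Table 5, both of which serve the case-control analysis.

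**Step 2. Is there a figure to reproduce?** No. The secondary objectives are descriptive without a power calculation, and the protocol gives neither immigration numbers nor a share of imported cases. What follows is illustration on assumed inputs.

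**Step 3. Effect on a before/after comparison.** Let d be the true decline, i0 and i1 the imported-case rates before and after introduction as fractions of the true pre-vaccine rate, and e any inflation of the early rate by residents' old disease first recorded when the series starts. Then

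recorded after/before ratio = ((1 − d) + i1) / (1 + i0 + e).

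With d = 50% and e = 0:

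- i 2% → 2%: 0.52/1.02 = 0.510, recorded change −49.0%
- i 2% → 5%: 0.55/1.02 = 0.539, −46.1%
- i 5% → 10%: 0.60/1.05 = 0.571, −42.9%
- i 5% → 20%: 0.70/1.05 = 0.667, −33.3%
- i 10% → 30%: 0.80/1.10 = 0.727, −27.3%

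With no true decline, 5% → 20% gives 1.20/1.05 = 1.143, a false rise of 14.3%. To hide a 50% fall completely with i0 = 0, i1 must be 0.5, so that imported cases are 0.5/(0.5 + 0.5) = half of all cases counted after introduction.

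**Step 4. The opposing effect.** With d = 50% and e = 20%:

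- i 2% → 5%: 0.55/1.22 = 0.451, −54.9%, so the fall is overstated
- i 5% → 20%: 0.70/1.25 = 0.560, −44.0%

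The net direction therefore depends on two unknowns.

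**Step 5. The same question from arrivals.** Take the AoRRP incidence of 0.5 per 100,000 that Section 5 gives for Denmark and Norway. Assume P prevalent cases per 100,000 arrivals and a yearly arrival share a of the age group. Recorded rate = true rate + P × a. With a true 30% fall, 0.50 becomes 0.35:

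- P = 3, a 1% → 2%: 0.53 → 0.41, −22.6%
- P = 5, a 1% → 2%: 0.55 → 0.45, −18.2%
- P = 5, a 1% → 3%: 0.55 → 0.50, −9.1%
- P = 10, a 1.5% → 3%: 0.65 → 0.65, no change
- P = 10, a 1% → 3%: 0.60 → 0.65, +8.3%

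These inputs are harsher than those in step 3. In step 3's terms, P = 3 with a 1% → 2% is already i0 = 0.03/0.5 = 6% and i1 = 0.06/0.5 = 12%. P = 10 with 1.5% → 3% is 30% and 60%. A prevalence of 10 per 100,000 equals 10/0.5 = 20 years of incidence, longer than the whole 15-29 age window.

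**The case against.** The broad population is defensible. A national incidence rate ordinarily covers every resident, the series has no exposure to misclassify, and the analysis is descriptive. All of that stands, and it is a reason to keep the all-resident series. It does not make a first local record a new case.

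Not every prevalent arrival would be counted. Section 5 calls RRP generally benign and self-limiting, and where pathology codes are required a local pathology record may be needed. This reduces the size of the bias without removing it. The expert case-profile review in Section 7.6 is unlikely to do so either, because only structured registry data are used and Section 7.13 concedes that full medical detail is lacking.

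There are partial internal checks. Male coverage was very low, so drift from imported cases might also show in men, although herd effects and the sex mix of arrivals limit the comparison. Tables are country-specific. Norway's series begins in 2008 and its programme in 2009, so little before/after contrast is available there in any case.

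A reader might infer that the protocol itself reports a growing share of imported disease, and that the series will therefore mask a decline. The documents do not support this. Section 7.13 says only that immigration was high, especially after introduction, and says nothing about the share of cases or of person-time without history. In the illustrations a fall disappears only at the most extreme prevalence assumed.

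Nor is this simply detail left to an analysis plan: Section 7.4 fixes eligibility and expressly confines the rule to the primary objective.

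**Conclusion.** The point holds as an inconsistency in scope. The protocol recognises that short registry history makes new onset uncertain, guards the primary analysis against it, and leaves unguarded the series whose numerator is new cases. Followed as written, the plan counts disease first diagnosed abroad as new and can place juvenile-onset disease in AoRRP.

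The effect on the trend is probably toward a smaller decline, given the statement on immigration in Section 7.13, but that direction is an inference. Under the assumed imported rates in step 3, a true 50% fall is recorded as 27-49%. Inflation at the start of the series could offset or reverse this, so neither the size nor the net direction can be fixed from the protocol. What is affected is a secondary, descriptive estimate and its trend test. The odds ratio of the primary objective is untouched.

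**What to change.** In Sections 7.4 and 7.11, keep the all-resident series as the national rate and add a prespecified restricted series. Apply the restriction identically to cases and to person-time, and report the calendar-year trend test on both series.

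- **AoRRP:** restrict to persons born in the country or arrived by age 9, which matches the history used in the primary analysis.
- **JoRRP:** restrict to persons born in the country, or set a minimum residence before a first diagnosis counts as new. The age-9 cut does not work here. Section 5 puts most JoRRP diagnoses at ages 2-4, so a child diagnosed abroad at 3 who arrives at 6 would still be counted as new.

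The restriction deals with imported disease (i0 and i1 above). It does not remove old disease in residents first recorded when the series starts, and the report should say so.

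The cost is protocol wording and one further run of the incidence tables. Section 7.7 already lists migration data for the population registry of each country. The downside is some lost person-time and a second series that does not cover every resident.

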7.5 Stratification

Stratified analyses, statistical adjustment, and/or assessment of interaction will be performed for the primary objective according to the following factors:

- 1) Age at vaccination (girls/women vaccinated before 17 years of age or after 17 years of age compared to unvaccinated). Primary objective/analysis will focus on evaluation of vaccine effectiveness among females vaccinated before 17 years of age.
- 2) Personal history of external genital warts (yes/no).

PRODUCT: V501/V503	PROTOCOL/AMENDMENT VERSION NO.: V503-088-01-v1
REVOPS ID NO: NIS009722	CORE DRC APPROVAL DATE: 18JUL2024
EPIDEMIOLOGY NO.(PE STUDIES ONLY): EP08039.017	

Stratified analyses for the secondary objective will be performed according to calendar year, gender, and age.

7.6 Variables

All the below variables are intended to be analyzed as categorical variables for primary analysis. Where applicable, continuous covariates such as income or number of years of education, will be categorized into standard categories.

Validation: Analyses will be carried out using the ICD-10 code D14.1 (benign tumor of the larynx), and if needed, the equivalent codes to D14.1 in the predecessor ICD system ICD-9 and ICD-7. In countries where available/complete from the pathology/cancer registry, appropriate topography/morphology or SNOMED/Norpat codes (identified in consultation with sub-specialist clinical experts) will also be used to increase specificity of the outcome definition in primary analyses, as discussed in Section 7.1 (Case definition) above. Specificity may also be increased by using ICD-10 code D14.1A, when available. Descriptive statistics of the combinations of diagnostic and procedural codes for all the cases in the dataset will be provided. Study investigators will further work with local clinician expert(s) as needed, to investigate and define which combination of procedural codes (e.g., DQB10, UDQ25, or UDW22) for RRP may provide further specificity to validate the outcome. Depending on exact case numbers available from the registries, the plan is to perform this procedure for all cases identified.

Otorhinolaryngologists/phoniatricians as well as other experts in RRP, HPV, epidemiology, and biostatistics external to the study have provided valuable input on the study design and case ascertainment and will continue to be consulted as needed throughout the study. These experts will play an important role in the validation process, performing case profile review (blinded to vaccination status) to ensure accurate identification and characterization of AoRRP cases. A Scientific Review Committee with expertise in RRP, HPV, epidemiology, and biostatistics has been formed to provide an independent review of study findings, including interpretation of results.

7.6.1 Exposure

A subject will be defined as fully vaccinated and exposed if she has received 2 or 3 doses (depending on age group-specific dose regimen recommendation) of HPV vaccine with GARDASIL or GARDASIL 9 as defined through the ATC code J07BM01 or J07BM03. Among individuals who initiated vaccination prior to 15 years of age, receipt of 2 doses administered at 0 and 6-12 months is considered fully vaccinated, whereas among individuals who initiate vaccination after 15 years of age, 3 doses administered at 0, 2, and 6 months is considered fully vaccinated. Sensitivity analysis will be performed where individuals will be classified as exposed/vaccinated if they received at least one vaccine dose. The study primary objective/analysis will focus on evaluation of vaccine effectiveness among females fully vaccinated before age 17 years. A female will be classified as unexposed if she did not receive even a single dose of Gardasil prior to being selected as a case or control in the study. Sensitivity analyses will be performed evaluating effectiveness irrespective of age at vaccination, and among those vaccinated at older ages (≥17 years).

PRODUCT: V501/V503	PROTOCOL/AMENDMENT VERSION NO.: V503-088-01-v1
REVOPS ID NO: NIS009722	CORE DRC APPROVAL DATE: 18JUL2024
EPIDEMIOLOGY NO.(PE STUDIES ONLY): EP08039.017	

7.6.2 Outcomes

Detailed case definitions for primary and secondary objectives for each participating country are provided in Section 7.1.

Nested case-control study (primary objective)

Definition of AoRRP case: A subject will be defined as having a first case of AoRRP if she has ≥1 hospitalization or outpatient record with diagnosis registered as ICD-10 code D14.1 along with appropriate topography/morphology or SNOMED/Norpat codes as deemed necessary by experts, between 15-29 years of age [33].

Selection of controls: random selection of 10 controls per case from the underlying population at risk in the respective countries, using incidence density sampling procedures. Matching criteria will be age at diagnosis, calendar year, region where case was diagnosed, and length of follow-up.

Ecological study (secondary/exploratory objective)

- All subjects will be defined as having a case of JoRRP if he/she has ≥1 hospitalization or outpatient record with diagnosis registered as D14.1 along with appropriate topography/morphology or SNOMED/Norpat codes as deemed necessary by experts, with a first diagnosis of this condition before 15 years of age.
- All subjects will be defined as having a case of AoRRP if he/she has ≥1 hospitalization or outpatient record with diagnosis registered as D14.1 along with appropriate topography/morphology or SNOMED/Norpat codes as deemed necessary by experts, with a first diagnosis of this condition after 15 years of age and before 30 years of age.

7.6.3 Covariates

In an observational study, where exposure is not randomized, it is important to explicitly express which association is being investigated, and a priori motivate which covariates are proposed for inclusion/exclusion and why. To this end, an Annex to this Protocol has been prepared which lists in detail subject matter expertise reasoning and motivation regarding potential confounders, specifically for the proposed association of study: potential effectiveness of HPV vaccination against AoRRP. Therein, a closer discussion on variables of consideration, the size of associations when known, and potential causal mechanisms supporting a confounding theory are discussed (Annex 1). For all covariates, missing data will be labeled as "Missing" and included as a separate category in the statistical analysis.

PRODUCT: V501/V503	PROTOCOL/AMENDMENT VERSION NO.: V503-088-01-v1
REVOPS ID NO: NIS009722	CORE DRC APPROVAL DATE: 18JUL2024
EPIDEMIOLOGY NO.(PE STUDIES ONLY): EP08039.017	

Covariates (potential confounders and/or effect modifiers):

- 1) Genital warts: External genital warts (EGW) or anogenital warts (AGWs) are, like RRP, caused by HPV6 and HPV11. History of EGWs is therefore expected to be a strong risk factor for RRP, with HPV6/11 infection being the likely causative agent for both conditions. It is important to consider that adjustment for EGWs may attenuate the estimated vaccine effect on RRP because some of the vaccine effect on RRP may be attributed to the EGW covariate. It is also possible that maternal history of EGWs may be associated with risk of AoRRP. An individual will be defined as having EGWs based on ≥1 hospitalization or outpatient record with diagnosis registered as A63 with subcodes, and/or a prescription for a pharmaceutical against anogenital warts (ATC codes D06BB10 [imiquimod] and/or D06BB04 [podophyllotoxin], as validated in Levàl et al, 2012 and Herweijer et al, 2014) [31] [34].
- 2) History of chlamydia infection: EGW is the only sexually transmitted disease which may be comprehensively investigated in Swedish and Danish registries; the other STDs such as *Chlamydia trachomatis* (CT), gonorrhea, or syphilis are protected by law which limits the possibility of tracing individuals with a history of such diagnoses. It is possible to study certain antibiotics such as doxycycline which is drug of choice in treatment of genital CT infection, however this drug is also used in some cases of upper respiratory tract infection in the age group of this study entailing poor specificity of this as proxy for genital infection. In a subset of study population from Norway, Chlamydia infections will be retrieved from the Norwegian Prescription Database based on treatment with doxycycline (ATC code J01AA02).
- 3) Age at vaccination (before 17 years of age vs 17 years or older): Given the importance of age at vaccination (i.e., vaccination is exclusively prophylactic, and risk of HPV exposure increases with age), the primary objective is focused on evaluation of effectiveness among females fully vaccinated before 17 years of age.
- 4) Education level of subject/mother (highest level achieved) will be categorized as low/medium/high according to the Swedish, Danish, and Norwegian system of number of school years.
- 5) Annual individual/family income will be categorized in tertiles or quantiles relative to the general female population of the respective Nordic country and corresponding age structure from the KI team's previous study on HPV vaccine uptake in relation to parents' country of birth, education and income, there were 2.2%, 3.9% and 3.1% missing data for mothers and 4.2%, 6.6% and 6.4% missing data for fathers, respectively [35]. Overall, missing data in this specific field represented a small but definable category which is feasible to be studied as a measure of study participants who are e.g., underserved or lack demographic information due to immigration.

